1.1. Schedule of Events

1.1.1. First Single Dose, Cohorts 1A, 1B, 2A, 2B, 3A, and 3B

Table 1: Schedule of Events: First Single Dose, Cohorts 1A, 1B, 2A, 2B, 3A, and 3B

Day (Window)	Screening	Clinical Research Unit (CRU) Inpatient Stay										Outpatient CRU Visits ^a			
		-28 to -2	-1	1	2	3-6	7	9	11	14	21	OV1 (±3)	OV2 (±5)	OV3 (±7)	OV4 ^b (±14)
Informed consent	X														
Inclusion/Exclusion criteria ^c	X	X													
Medical history/demographics	X														
Complete physical with vital signs (BP, RR, HR, oral temperature, height, weight, BMI)	X														
Targeted physical with vital signs (BP, RR, HR, oral temperature)		X	X ^d	X	X	X				X	X	X	X	X	X
Safety ECG ^e	X	X	X				X					X			X
Holter Monitor ECG ^f			X	X	X										
Laboratory evaluations (CBC with/platelets, serum chemistry, urinalysis)	X	X		X	X ^g	X				X	X	X	X	X	X
Lipids, coagulation, complement activation ^h	X														
Virology screening (HBV, HCV, HIV)	X														
Virology screening (SARS-CoV-2)		X													
Serum/urine pregnancy test, FSH ⁱ	X	X										X	X	X	X
Drug/alcohol screen ^j	X	X													
Randomization		X													
Dosing of study drug			X												
Reactogenicity/injection site inspection ^k			X	X	X										
PK sample collection ^l			X	X	X	X	X	X	X	X	X	X	X	X	X
Samples for metabolite identification and CD388 DAR distribution ^m			X	X						X		X			X
Samples for CD388 glycoforms ⁿ			predose	X		X				X	X	X	X		X

Day (Window)	Screening	Clinical Research Unit (CRU) Inpatient Stay											Outpatient CRU Visits ^a			
		-28 to -2	-1	1	2	3-6	7	9	11	14	21	30	OV1 (± 3)	OV2 (± 5)	OV3 (± 7)	OV4 ^b (± 14)
Pharmacogenomics blood sample ^c			predose													
Exploratory biomarker samples			predose			X ^g										
Anti-drug antibodies			predose							X		X	X	X	X	X
Nasopharyngeal swab collection ^p			predose	X	X	X	X	X	X	X	X					
Assess and record AEs ^q	X	X	X	X	X	X	X	X	X	X	X	X	X	X	X	X
Concomitant medications/procedures review ^r	X	X	X	X	X	X	X	X	X	X	X	X	X	X	X	X

Abbreviations: AEs = adverse events; BMI = body mass index; BP = blood pressure, CBC = complete blood count; COVID-19 = coronavirus disease 2019; CRU = clinical research unit; DAR = drug-antibody ratio; ECG = electrocardiogram; FSH = follicle-stimulating hormone; HBV = hepatitis B virus; HCV = hepatitis C virus; HIV = human immunodeficiency virus; HR = heart rate; hr = hour; ICF = informed consent form; OV = outpatient visit; PK = pharmacokinetic; RR = respiration rate; SARS-CoV-2 = severe acute respiratory syndrome coronavirus 2.

Schedule of Events: First Single Dose, Cohorts 1A, 1B, 2A, 2B, 3A, and 3B

- For subjects in Cohorts 1A and 1B: outpatient visits will occur at Day 45 (OV1), Day 60 (OV2), Day 90 (OV3), and Day 120 (OV4). For subjects in Cohorts 2A, 2B, 3A, and 3B, timing of outpatient visits will occur at Day 45 (OV1), $\sim 2 \times t_{1/2}$ (OV2), $\sim 3 \times t_{1/2}$ (OV3), and $\sim 4 \times t_{1/2}$ (OV4), pending PK data from Cohorts 1A and 1B. If 2 half-lives have passed by OV2, the visit may be omitted.
- For subjects who discontinue study early, the OV4 procedures should be performed.
- For subjects in Cohorts 2A, 2B, 3A, and 3B, reconfirmation of inclusion and exclusion criteria (retesting of FSH not required) is to be completed at second single dose period's CRU check-in and prior to the second single dose of CD388 Injection or placebo.
- On Day 1, the targeted physical examination should be performed predose. Vital signs collection will occur predose, 6 hours postdose, and as clinically indicated.
- 12-lead ECG is to be performed at screening, at CRU check-in on Day -1, predose (immediately prior to study drug administration) and 6 hours postdose (± 10 minutes) on Day 1, and as indicated in the Schedule. Subjects are to be resting and semi-recumbent when ECG is being conducted.
- For Cohorts 1A, 1B, 2A, 2B, 3B: Continuous 12-lead digital ECG recording will be performed using a 12-lead Holter ECG monitor. Pharmacodynamic ECG tracings, including all 12-leads and of 10 seconds duration, will be extracted in triplicate for 5-minute observation periods at 60, 45, and 30 minutes predose; and at 2, 4, 6, 8, 10, 12, 24, 30, 36, and 48 hours postdose (expected time to maximum concentration is 1 to 2 days after administration). The Holter monitor will be removed on Day 3. The Holter monitor may be removed once on Day 2 for up to 15 minutes for shower/bathing, at least 2 hours away from the next ECG timepoint (i.e., 30, 36, or 48 hours postdose).
For Cohort 3A: Continuous 12-lead digital ECG recording will be performed using a 12-lead Holter ECG monitor. Pharmacodynamic ECG tracings, including all 12 leads and of 10 seconds duration, will be extracted in triplicate at prespecified time points for a 5-minute observation period starting from 1 hour before dosing, then at 72, 76, 80, 84, 96, 102, 106, 110, 118, and 120 hours after administration of study drug, and stored in a digital format. The Holter monitor may be removed once on Day 5 for up to 15 minutes for shower/bathing, at least 1 hour away from the next ECG timepoint. The Holter monitor will be removed on Day 6.

Schedule of Events: First Single Dose, Cohorts 1A, 1B, 2A, 2B, 3A, and 3B (continued)

- g. Laboratory evaluations need to be performed once during the Day 3–6 interval.
- h. Performed at screening, and as clinically indicated (e.g., if the Investigator has concerns regarding an SAE, anti-drug antibody reaction in a subject with hypersensitivity reaction, fever, serious rash, joint/bone pain, cough, proteinuria, or clinically meaningful changes in the white cell differential or liver function tests).
- i. A sensitive serum pregnancy test (β -human chorionic gonadotropin) is required at screening and OV4 for females of childbearing potential. FSH (if applicable to confirm postmenopausal status) is only required once. Urine pregnancy test may be performed at all other time points.
- j. Drug and alcohol screen is to be performed during the outpatient visits if vital signs are abnormal (see [Appendix 2](#)).
- k. At indicated visits, inspection of administration site and surrounding area will be performed twice daily (once between approximately 2–4 hours postdose, and once approximately 8–12 hours postdose), with any abnormal findings reported as AE s. Reactions will be rated according to the scale provided in [Table 7](#).
- l. For Cohorts 1A, 1B, 2A, 2B, 3B: Blood samples for PK analysis will be collected predose (-24 hour window); post-dose at 2, 4, and 12 hours (each \pm 10 minute window); 24 hours (\pm 30 minute window); 48 hours (\pm 1 hour window); 72, 96, 120 hours (each \pm 2 hour window); and Days 7, 9, 11, 14, 21, 30 (each \pm 2 hour window). Postdose samples collected at outpatient CRU visits at OV1, OV2, OV3, and OV4 have the same windows (i.e., in \pm days) as the visits.
For Cohort 3A: Blood samples for PK analysis will be collected predose (-24 hour window); post-dose at 12 and 24 hours (\pm 30 minute window); 48 hours (\pm 1 hour window); 72, 84, 96, 108, 120 hours (each \pm 2 hour window); and Days 7, 9, 11, 14, 21, 30 (each \pm 2 hour window). Postdose samples collected at outpatient CRU visits at OV1, OV2, OV3, and OV4 have the same windows as the visits.
- m. Blood samples for metabolite identification (e.g., free zanamivir, zanamivir dimers) and CD388 DAR distribution will be collected on Day 1 at 2 hours postdose, on Day 2 at 24 hours postdose, on Days 14 and 30, and at OV3. Urine samples for metabolite identification will be collected on Day 1 from 0–12 hours and from 12–24 hours postdose, on Day 2 from 24–48 hours postdose, on Day 14 over a 24-hour period, and over a 24-hour period that starts on Day 29 and ends prior to CRU check-out on Day 30.
- n. Serum samples for CD388 glycoforms will be collected predose on Day 1 and once in the morning on Days 2, 7, 14, 21, and 30, and at the OV1 and OV3 visits.
- o. A mandatory pharmacogenomic (DNA) blood sample will be collected once, preferably on Day 1 (collection at another time point is allowed if necessary) to allow for pharmacogenomic research related to CD388.
- p. Nasopharyngeal swab samples will be collected predose on Day 1, and on Days 2, 5, 7, 9, 11, 14, 21, and 30.
- q. Adverse events (including influenza-like illness which will be tested for both COVID-19 and flu) will be collected for all subjects from the time of signing the ICF through 4 months after the last dose of study drug, whichever is longer.
- r. Concomitant procedures used to treat an AE will be recorded from the time of CD388 Injection/placebo administration until the final study visit.

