- d. On Day 1, the targeted physical examination should be performed predose. Vital signs collection will occur predose, 6 hours postdose, and as clinically indicated.
- e. 12-lead ECG is to be performed at CRU check-in on Day -1, predose (immediately prior to study drug administration on Day 1) and 6 hours postdose (± 10 minutes), and as indicated in the Schedule. Subjects are to be resting and semi-recumbent when ECG is being conducted.
- f. Laboratory evaluations need to be performed once during the Day 3–6 interval.
- g. Urine pregnancy test is required for females of childbearing potential at CRU check-in on Day -1.
- h. Drug and alcohol screen is to be performed during the outpatient visits if vital signs are abnormal (see [Appendix 2](#)).
- i. At indicated visits, inspection of administration site and surrounding area will be performed twice daily (once between approximately 2–4 hours postdose, and once approximately 8–12 hours postdose), with any abnormal findings reported as AEs. Reactions will be rated according to the scale provided in [Table 7](#).
- j. Blood samples for PK analysis will be collected predose (-24 hour window); post-dose at 24 hours (± 30 minute window); 48 hours (± 1 hour window); 72, 96, 120, 144, 168 hours (each ± 2 hour window); and Days 9, 10, 11, 12, 14, 21, 30 (each ± 2 hour window). Postdose samples collected at outpatient CRU visits on Days 45, 60, 90, and 120 have the same windows (i.e., in \pm days) as the visits.
- k. Blood samples for metabolite identification (e.g., free zanamivir, zanamivir dimers) will be collected on Day 1 at 2 hours postdose, on Day 2 at 24 hours postdose, on Day 30, and on Day 90. Urine samples for metabolite identification will be collected on Day 1 from 0–48 hours, from 48–96 hours, and from 96–144 hours postdose, on Day 14 over a 24-hour period, and over a 24-hour period that starts on Day 29 and ends prior to CRU check-out on Day 30.
- l. Nasopharyngeal swab samples will be collected predose on Day 1, and on Days 2, 5, 7, 9, 11, 14, 21, and 30. Nasal wash collection will occur at the time of C_{max} as determined from the first single dose (approximately 144 hours after dosing).
- m. Adverse events (including influenza-like illness which will be tested for both COVID-19 and flu) will be collected for all subjects as indicated below:

Cohort	AE/SAE monitoring period from signing of Informed Consent Form:
1A, 1B	Through 4 months after the dose of study drug

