[figure not shown]
Schedule of Events: Single Dose, Cohort 4B

- For subjects who discontinue study early, the Day 206 procedures should be performed.
- On Day 1, the targeted physical examination should be performed predose. Vital signs collection will occur predose, 6 hours postdose, and as clinically indicated.
- 12-lead ECG is to be performed at screening, at CRU check-in on Day -1, predose (immediately prior to study drug administration) and 6 hours postdose (± 10 minutes) on Day 1, and as indicated in the Schedule. Subjects are to be resting and semi-recumbent when ECG is being conducted.
- Continuous 12-lead digital ECG recording will be performed using a 12-lead Holter ECG monitor. Pharmacodynamic ECG tracings, including all 12-leads and of 10 seconds duration, will be extracted in triplicate for 5-minute observation period starting from 1 hour before dosing, then at 72, 76, 80, 84, 96, 102, 106, 110, 118, and 120 hours after administration of study drug, and stored in a digital format. The Holter monitor will be removed on Day 6. The Holter monitor may be removed once on Day 5 for up to 15 minutes for shower/bathing, at least 1 hour away from the next ECG timepoint.
- Laboratory evaluations need to be performed once during the Day 3–6 interval.
- Performed at screening, and as clinically indicated (e.g., if the Investigator has concerns regarding an SAE, anti-drug antibody reaction in a subject with hypersensitivity reaction, fever, serious rash, joint/bone pain, cough, proteinuria, or clinically meaningful changes in the white cell differential or liver function tests).
- A sensitive serum pregnancy test (β -human chorionic gonadotropin) is required at screening and OV4 for females of childbearing potential. FSH (if applicable to confirm postmenopausal status) is only required once. Urine pregnancy test may be performed at all other time points.
- Drug and alcohol screen is to be performed during the outpatient visits if vital signs are abnormal (see [Appendix 2](#)).
- At indicated visits, inspection of administration site and surrounding area will be performed twice daily (once between approximately 2–4 hours postdose, and once approximately 8–12 hours postdose), with any abnormal findings reported as AEs. Reactions will be rated according to the scale provided in [Table 7](#).

Schedule of Events: Single Dose, Cohort 4B (continued)

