3A	Predose from 1 hour before administration of first single dose until administration is complete, and from 72 to 120 hours after dosing ^a
4B	Predose from 1 hour before administration of single dose until administration is complete, and from 72 to 120 hours after dosing

Note: Timing of ECG monitoring has been adjusted for Cohort 3A and 4B based on PK and ECG data.

a. Performed at the second administration period only if required to further evaluate observations from prior peri-dosing period (at the discretion of the Investigator).

Blood PK samples, and blood samples to assess ADA will be collected from all subjects for the purpose of maintaining the blind, but only samples from the CD388 Injection group will be analyzed (using validated assays) by an unblinded central bioanalytical laboratory. After discharge from the CRU, additional sample collection for PK and ADA will be performed at specified time points after dosing. The timing of PK sampling has been adjusted for Cohorts 2A, 2B, 3A, and 3B based on data from previous cohorts.

Additional blood samples will be collected for pharmacogenomics and exploratory biomarker evaluation, and additional blood and urine samples will be collected for exploratory metabolite identification, to be reported separately. Plasma samples collected for PK analysis may also be used for CD388 drug-antibody ratio (DAR) distribution and metabolite identification after completion of PK analysis. Nasopharyngeal swabs will also be collected for CD388 exploratory assays. Nasal wash collection will occur during the second single dose at the time of C_{max} as determined from the first single dose. Nasal wash collection for Cohort 4B will occur during dosing on Day 7.

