
 To determine the PK profile of CD388 Injection in upper respiratory tract after IM or SQ administration as a single dose to healthy adult subjects. 	
 Pharmacokinetic parameters following CD388 Injection administration: maximum nasopharyngeal (NP) concentration (C_{max}), time to maximum NP concentration (T_{max}), area under the NP concentration-time curve from time 0 to time of last quantifiable sample (AUC_{0-t}). 	Refer to Section 7

 To identify CD388 metabolites in plasma, CD388 and its metabolites in urine, and CD388 drug-antibody ratio (DAR) distribution in plasma, and CD388 glycoforms in serum after IM or SQ administration to healthy adult subjects. 	
 CD388 metabolites (e.g., free zanamivir, zanamivir dimers) in plasma and urine, CD388 in urine and nasal wash, CD388 DAR distribution in plasma, and CD388 glycoforms in serum, to be reported separately. 	Refer to Section 7

 To evaluate biomarkers that may be associated with AEs after CD388 Injection. 	
 Results of the analyses of exploratory biomarkers (including but not limited to cytokines, chemokines, acute phase reactants, etc.). 	Refer to Section 9

 To evaluate CD388 immunogenicity. 	
 Anti-drug antibody titers in blood (plasma or serum). 	Refer to Section 9

 To explore pharmacogenomics related to CD388. 	
 Results of the analyses of pharmacogenomic samples, to be reported separately. 	Refer to Section 9

Objective	Endpoint	Analysis

 • To explore the effects on cardiac safety in subjects administered CD388 Injection. 	
 • 12-lead ECG and Holter monitoring parameters. 	Refer to Section 8

 • To explore the effect of CD388 injection on the occurrence of influenza-like illness (during flu season). 	
 • Influenza-like illness reporting during the outpatient follow-up period. 	Refer to Section 8

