8.4 Physical Examination Findings

The physical examination will include a general review of the following body systems: general appearance, HEENT, neck / thyroid, respiratory, cardiovascular, gastrointestinal, genitourinary, neurological, musculoskeletal / extremities, skin and other. Physical examination results, with abnormal and clinically significant abnormal findings flagged will be listed.

8.5 12-Lead ECG Analysis

12- Lead safety ECG results will be summarized descriptively by visit and timepoint and change from baseline will be presented. Data listings will identify if values are “abnormal, clinically significant” or “abnormal, not clinically significant”.

Outliers with respect to QTcF will also be tabulated for the following categories:

Absolute value > 450 msec and \leq 480 msec

Absolute value > 480 msec and \leq 500 msec

Absolute value > 500 msec

Increase from baseline \geq 30 msec and < 60 msec

Increase from baseline \geq 60 msec

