	Mean (SD)	xx.x (xx.xx)	xx.x (xx.xx)	xx.x (xx.xx)	xx.x (xx.xx)	xx.x (xx.xx)	xx.x (xx.xx)	xx.x (xx.xx)	xx.x (xx.xx)	xx.x (xx.xx)	xx.x (xx.xx)	xx.x (xx.xx)	xx.x (xx.xx)	xx.x (xx.xx)	xx.x (xx.xx)	xx.x (xx.xx)	xx.x (xx.xx)
	Median	xx.x	xx.x	xx.x	xx.x	xx.x	xx.x	xx.x	xx.x	xx.x	xx.x	xx.x	xx.x	xx.x	xx.x	xx.x	xx.x
	Minimum, Maximum	xx, xx	xx, xx	xx, xx	xx, xx	xx, xx	xx, xx	xx, xx	xx, xx	xx, xx	xx, xx	xx, xx	xx, xx	xx, xx	xx, xx	xx, xx	xx, xx
Day xx Pre-Dose	n	xx	xx	xx	xx	xx	xx	xx	xx	xx	xx	xx	xx	xx	xx	xx	xx
	Mean (SD)	xx.x (xx.xx)	xx.x (xx.xx)	xx.x (xx.xx)	xx.x (xx.xx)	xx.x (xx.xx)	xx.x (xx.xx)	xx.x (xx.xx)	xx.x (xx.xx)	xx.x (xx.xx)	xx.x (xx.xx)	xx.x (xx.xx)	xx.x (xx.xx)	xx.x (xx.xx)	xx.x (xx.xx)	xx.x (xx.xx)	xx.x (xx.xx)
	Median	xx.x	xx.x	xx.x	xx.x	xx.x	xx.x	xx.x	xx.x	xx.x	xx.x	xx.x	xx.x	xx.x	xx.x	xx.x	xx.x
	Minimum, Maximum	xx, xx, xx, xx, xx	xx, xx, xx, xx, xx	xx, xx, xx, xx, xx	xx, xx, xx, xx, xx	xx, xx, xx, xx, xx	xx, xx, xx, xx, xx	xx, xx, xx, xx, xx	xx, xx, xx, xx, xx	xx, xx, xx, xx, xx	xx, xx, xx, xx, xx	xx, xx, xx, xx, xx	xx, xx, xx, xx, xx	xx, xx, xx, xx, xx	xx, xx, xx, xx, xx	xx, xx, xx, xx, xx	xx, xx, xx, xx, xx
...

Date: VERSION - YYYY-MM-DD Data Source: xxx Program Source: xxxx.sas
 IM = Intramuscular; SQ = Subcutaneous; SD = Standard Deviation.

Note: Baseline is the measurement of the last predose measurement was used.

<Parameter (unit)> = ECG Mean Ventricular Rate (msec), PR Interval (msec), QRS Duration (msec), QT Interval (msec), QTcF Interval (msec)

<Programming Note>
ETC.= for SQ: Cohort 4B CD388 - Pooled Placebo . CD388 900 mg be added
It can be presented separately (i.e., IM one page and SQ another).

Table 14.2.25 Template T5.4: ECG: Maximum QTcF Categorical Analysis (Safety Population)

Table 14.3.4.2
ECG: Maximum QTcF Categorical Analysis
(Safety Population)

Nominal Day	Category	IM Route								SQ Route	
		CD388 50 mg (N = XX)	CD388 150 mg (N = XX)	CD388 450 mg (N = XX)	Pooled Placebo (N = XX)	CD388 50 mg (N = XX)	CD388 150 mg (N = XX)	CD388 450 mg (N = XX)	CD388 900 mg (N = XX)	ETC. (N = XX)	
Day xx	Absolute Values	n	xx	xx	xx	xx	xx	xx	xx	xx	
		> 450 msec and	xx	xx	xx (xx..x)	xx	xx (xx..x)	xx	xx (xx..x)	xx (xx..x)	
		≤ 480 msec	(xx..x)	(xx..x)		(xx..x)		(xx..x)			
		> 450 msec and	xx	xx	xx (xx..x)	xx	xx (xx..x)	xx	xx (xx..x)	xx (xx..x)	
		≤ 500 msec	(xx..x)	(xx..x)		(xx..x)		(xx..x)			
		> 500 msec	xx	xx	xx (xx..x)	xx	xx (xx..x)	xx	xx (xx..x)	xx (xx..x)	
			(xx..x)	(xx..x)		(xx..x)		(xx..x)			

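### SAP Section 8 plans no analysis of the Holter recordings that SAP Table 1 refers to it, and the QTcF outlier shell contradicts the bands in SAP 8.5

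*Protocol*

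**What the plan says.** **Endpoint.** Protocol Section 5 and SAP Table 1 set an exploratory cardiac-safety objective whose endpoint is "12-lead ECG and Holter monitoring parameters". SAP Table 1 sends it to Section 8.

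**Collection.** Protocol Table 1 footnote f and Section 9.4 have 10-second 12-lead tracings extracted from the Holter in triplicate.
- Cohorts 1A, 1B, 2A, 2B and 3B: 60, 45 and 30 minutes predose, then ten times from 2 to 48 h, with the note "expected time to maximum concentration is 1 to 2 days after administration". Section 9.4 lets this monitoring run longer or shorter as PK data emerge.
- Cohorts 3A and 4B: from 1 hour predose, "then at 72, 76, 80, 84, 96, 102, 106, 110, 118, and 120 hours after administration of study drug". Section 6.1 says that this shift was made on PK and ECG data.
- Holter at the second dose is at the Investigator's discretion (Section 6.1).

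**Peak time.** Protocol Table 2 footnote l times the nasal wash at Cmax, "as determined from the first single dose (approximately 144 hours after dosing". For the single-dose 900 mg cohort, Section 6.1 says "Nasal wash collection for Cohort 4B will occur during dosing on Day 7".

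**Analysis.** SAP 8.5 covers one source of ECG data: "Lead safety ECG results will be summarized descriptively by visit and timepoint". It then lists QTcF outlier bands, the middle one beginning "Absolute value > 480 msec and" and closing at ≤500 msec. The only shell for these bands is Table 14.3.4.2, "ECG: Maximum QTcF Categorical Analysis".

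**The concern.** A stated endpoint is cross-referenced to a section that does not contain it. Protocol Section 9.4 calls the Holter tracings pharmacodynamic, and Protocol Section 12 promises descriptive summaries of pharmacodynamics, but nothing in the SAP delivers them for Holter. Cardiac effect would then be reported only from Investigator-read safety ECGs, which after dosing are scheduled at 6 h, Day 7, Day 30 and the final visit.

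The second problem is that text and shell disagree on the outlier categories. If the shell is programmed literally, the table will not be the one that the SAP specifies, and its absolute rows will overlap. With 8 CD388 subjects per column, moving one subject between categories changes a percentage by 1/8 = 12.5 points.

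The third is that the protocol gives three accounts of when concentration peaks: 1 to 2 days, a Holter window shifted to 72–120 h, and about 144 h. Anyone interpreting Holter results needs to know which account applies and how far each window falls short of the peak.

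**Working it through.** **1. Where Holter goes**

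| Place | Content |
|---|---|
| SAP Table 1 | Names Holter, refers to Section 8 |
| SAP Table 6, ECG row | Interpretations, listings, parameter summaries, QT/QTc categories; Holter not named |
| SAP 8.5 | Safety ECG only |
| Tables 14.3.4.1 and 14.3.4.2, Listing 16.2.8.2.2 | ECG values by visit; no Holter times, triplicate averaging or Holter baseline |
| Protocol 12.5, SAP 9 | Items to be reported separately; Holter not among them |

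Volume: both schedules have ten postdose extraction times, so 10 × 3 tracings × 77 subjects = 2,310 postdose tracings without an assigned output. The cohort arithmetic agrees with the protocol: 7 × (8 + 3) = 77 subjects and 7 × 8 = 56 on CD388.

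**2. QTcF bands (msec)**

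| Band | SAP 8.5 | Shell 14.3.4.2 | Protocol Appendix 2 |
|---|---|---|---|
| Lower absolute | >450 to ≤480 | >450 to ≤480 | 450 to ≤480 men; 470 to ≤480 women |
| Middle absolute | >480 to ≤500 | >450 to ≤500 | 481 to ≤500 |
| Top absolute | >500 | >500 | >500 |
| Lower change | ≥30 to <60 | >30 to ≤60 | 30 to ≤60 |
| Top change | ≥60 | >60 | >60 |

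Test values:
- 465 msec falls in two shell rows.
- An increase of 60 is in the top category under SAP 8.5 and the lower one under the shell and Appendix 2.
- An increase of 30 is counted by SAP 8.5 and Appendix 2 but not by the shell.
- A woman at 460 is in the SAP's lower band but below the Appendix 2 borderline limit.

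The overlap can be undone: n(>450 to ≤500) − n(>450 to ≤480) = n(>480 to ≤500). No subtraction repairs the change bands. The overlap appears in both Day blocks of the shell, so it is unlikely to be a text-extraction fault.

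**3. Timing**

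Nominal hour = (Day − 1) × 24, so Day 3 = 48 h, Day 6 = 120 h and Day 7 = 144 h. Day 30 = 696 h, which matches the PK shells. The gap from the end of Holter to 144 h is:
- 144 − 48 = 96 h in five cohorts (5 × 8 = 40 of 56 CD388 subjects, 71%);
- 144 − 120 = 24 h in 3A and 4B (16 of 56, 29%).

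The 144 h figure cannot be re-derived, because the documents give no PK data. To size the gap, assume one compartment with first-order absorption:

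C(t)/Cmax = [exp(−ke·t) − exp(−ka·t)] / [exp(−ke·Tmax) − exp(−ka·Tmax)], with ke = ln 2 / half-life and ka solving ln(ka/ke)/(ka − ke) = Tmax.

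Take Tmax = 6 days and half-life = 42 days. The half-life is inferred: second-dose visits on Days 84, 126 and 168 are 2, 3 and 4 × 42, matching the half-life multiples used to time first-dose visits. Then ke = 0.0165/day and ka = 0.621/day.
- 48 h: (0.9675 − 0.2888)/(0.9057 − 0.0241) = 0.770.
- 120 h: (0.9208 − 0.0448)/(0.9057 − 0.0241) = 0.994.

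Over Tmax 5–7 days and half-life 18–60 days, the ranges are 64–86% at 48 h and 96–100% at 120 h.

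**4. What a Holter analysis could use**

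Nominal times shared with PK sampling are 2, 4, 12, 24 and 48 h in the 48 h cohorts (5 of 10) and 72, 84, 96 and 120 h in 3A and 4B (4 of 10). The two schedules share no postdose extraction time. Placebo on the 72–120 h schedule is 3 (3A) + 3 (4B) = 6. Pooled within route, only 3 of 12 SQ and 3 of 9 IM placebo subjects are on it.

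**The case against.** The objective is exploratory and descriptive, and its endpoint includes the 12-lead ECG. A safety ECG is scheduled on Day 7, nominally 144 h, in both dose periods and in 4B, and SAP 8.5 summarises it with change from baseline and QTcF categories. That stands. A reader might infer that the cardiac objective cannot be answered, and the documents do not support this. The Day 7 reading is a limited check, though: it is Investigator-read and no triplicate extraction is specified.

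SAP Table 6 heads its ECG row as 12-lead digital electrocardiograms, close to the protocol's wording for Holter, and the shells have visit and timepoint columns that could hold Holter rows. This does not fill the gap. The row's content matches safety ECGs, and no averaging rule or Holter baseline is given.

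A reader might also infer that the 900 mg window misses the peak and should be moved. The modelled level at 120 h is 96–100% of Cmax, the window was set on data that we cannot see, and moving it would break the match with the 3A placebo schedule.

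For the 48 h cohorts, the 1-to-2-day statement was an expectation. Protocol Section 4.3 reports 66 subjects already dosed at 50–450 mg, so those first-dose recordings cannot now be changed. If exposure is dose-proportional (an assumption), 900 mg at 120 h is about 1.93–2.00 times the 450 mg Cmax, so a concentration-based analysis would still reach high exposures.

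The shell error is small. SAP 8.5 has the correct non-overlapping absolute bands, the 481–500 msec count is recoverable by subtraction, and Listing 16.2.8.2.2 prints individual QTcF values. Finally, pooled placebo is not an error in any existing Holter display, because none is specified; it matters only once one is added.

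**Conclusion.** Two defects stand on the text alone. The Holter half of the cardiac-safety endpoint has no analysis, shell or listing, although SAP Table 1 says that Section 8 provides one; this affects recordings from all 77 subjects. Shell Table 14.3.4.2 contradicts SAP 8.5 in one absolute band and both change bands, so 451–480 msec is counted twice and an increase of exactly 60 msec is classified differently. Protocol Appendix 2 differs again.

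Timing is a limitation to declare. It is material in the five cohorts that end at 48 h (about 64–86% of Cmax) and small in 3A and 4B (about 96–100% at 120 h). Those percentages rest on the assumed one-compartment model, Tmax of 5–7 days and half-life of 18–60 days; the documents give no Tmax by route or dose. The objective is under-analysed, and correction is worthwhile because it changes what is reported without any new procedure.

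**What to change.** (a) Correct Table 14.3.4.2 to non-overlapping bands that match SAP 8.5. Reconcile the 30 and 60 msec boundaries and the sex-specific borderline limits between SAP 8.5 and Protocol Appendix 2, so that all three sources agree.

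(b) Add to SAP 8.5, with a shell and a listing, Holter QTcF, HR, PR and QRS as the mean of triplicates and as change from a predose Holter baseline. State the baseline rule: the SAP 10.3 default takes the last predose value, which would use only one of the three predose extractions in the 48 h cohorts. Relate the changes to CD388 concentration at the nominal times shared with PK sampling (2, 4, 12, 24 and 48 h; or 72, 84, 96 and 120 h in 3A and 4B). In any by-time display, compare 3A and 4B only with the 6 placebo subjects recorded at 72–120 h, pooled across routes, and not with all placebo within a route.

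(c) Leave the 4B Holter window as it is. The sponsor should reconcile the three Tmax statements and report as a limitation that Holter in 1A, 1B, 2A, 2B and 3B ends at 48 h.

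The cost is SAP wording and programming, with no added procedure. The drawback is small numbers: 8 CD388 subjects per cohort and 6 time-matched placebo subjects, so the results stay descriptive.
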